4.2.5 Dose Modifications

Intra-patient dose reduction to 1.2 mg/kg will be allowed depending on the type and severity of toxicity. **Table 1** describes the recommended dose modifications for study treatment-associated toxicity (toxicity with suspected relationship to SGN-35).

Peripheral Neuropathy: Peripheral neuropathy should be managed using a combination of dose delay and reduction to 1.2 mg/kg. For new or worsening Grade 2 or 3 neuropathy, dosing should be held until neuropathy improves to Grade 1 or baseline and then restarted at 1.2 mg/kg. For Grade 4 peripheral neuropathy, SGN-35 should be discontinued.

A study of brentuximab vedotin (SGN-35) in CD30-positive systemic mastocytosis with or without an associated hematological clonal non-mast cell lineage disease (AHNMD)

Neutropenia: Neutropenia should be managed by dose delays and reductions. The dose of SGN-35 should be held for Grade 3 or 4 neutropenia until resolution to baseline or Grade 2 or lower. Growth factor support should be considered for subsequent cycles in patients who experience Grade 3 or 4 neutropenia. In patients with recurrent Grade 4 neutropenia despite the use of growth factors, discontinuation or dose reduction of SGN-35 to 1.2 mg/kg may be considered.

Acute Pancreatitis: Acute pancreatitis has been identified as an important potential risk associated with brentuximab vedotin dosing. Dosing should be held until a diagnosis of acute pancreatitis has been excluded if clinically suspected.

The start of the next cycle may be delayed for up to 30 days if additional time is required for the patient to recover from study treatment-associated toxicity experienced during the current cycle (**Table 1**). Delays of greater than 30 days are prohibited without approval of the Principal Investigator of the entire study, [name].

Doses reduced for treatment-related toxicity should not be re-escalated.

If 4 out of the 11 patients experience emergent drug-related Grade 3 or 4 non-hematologic toxicity, the study will be placed on hold for safety review, and if restarted upon study amendment, the starting dose of therapy for subsequent patients would be no more than 1.2 mg/kg.

Table 1. Dose Reduction Algorithms for Non-Hematologic and Hematologic Toxicity With Suspected Relationship to SGN-35

Toxicity	Grade 1	Grade 2	Grade 3	Grade 4

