Hematologic	Continue at same dose level.	Continue at same dose level.	
 The dose of SGN-35 should be held for Grade 3 or 4 neutropenia until resolution to baseline or Grade 2 or lower. Growth factor support should be considered for subsequent cycles in patients who experience Grade 3 or 4 neutropenia. In patients with recurrent Grade 4 neutropenia despite the use of growth factors, discontinuation or dose reduction of SGN-35 to 1.2 mg/kg may be considered. Dose interruption for anemia will not be undertaken. If patients have Grade 2 to 3 of these events at baseline only Grade 4 cytopenias suspected to be related to study drug will be considered as hematologic toxicity. ^b Obtain weekly labs until lab returns to baseline or Grade 2. G-CSF for treatment of neutropenic fever may be used, but not for treatment of neutropenia alone, nor for infection prophylaxis in the setting of neutropenia. 	

^a Patients who develop emergent Grade 3 or 4 electrolyte laboratory abnormalities will have the dose of SGN-35 reduced to 1.2 mg/kg in subsequent cycles. If the same Grade 3 or 4 electrolyte abnormalities re-occur, SGN-35 will be discontinued.

^b Patients who develop Grade 3 or 4 lymphopenia may continue study treatment without interruption.

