Ascites or pleural effusions	(1) Symptomatic ascites or pleural effusion requiring medical intervention such as use of diuretics (grade 2), OR (2) ≥ 2 therapeutic paracenteses or thoracenteses at least 28 d apart over 12 wk prior to study entry (grade 3), and one of the procedures is performed during the 6 wk prior to drug start	(1) Complete resolution of symptomatic ascites or pleural effusion* AND no longer in need of diuretic(s) for ≥ 12 wk, OR (2) No therapeutic paracentesis or thoracentesis for ≥ 12 wk
Liver function abnormalities	\geq Grade 2 abnormalities in direct bilirubin, AST, ALT, or AP† in the presence of ascites, and/or clinically-relevant portal hypertension, and/or liver MC infiltration that is biopsy-proven or other causes for abnormal liver function are not identified	Reversion of 1 or more liver function tests to normal range for ≥ 12 wk
Hypoalbuminemia	\geq Grade 2 hypoalbuminemia (< 3.0 g/dL)	Reversion of albumin to normal range for ≥ 12 wk
Symptomatic marked splenomegaly	Symptomatic marked splenomegaly: a spleen that is palpable > 5 cm below the left costal margin and the patient endorses symptoms of discomfort and/or early satiety	$\geq 50\%$ reduction in palpable splenomegaly and no endorsement of discomfort and/or early satiety for ≥ 12 wk (3D computed tomography/magnetic resonance imaging evaluation may also be undertaken.)
Hematologic		
ANC	Baseline grade ≥ 3 ANC ($< 1 \times 10^9/L$)	A minimum 100% increase in the ANC and an ANC of at least $0.5 \times 10^9/L$ for ≥ 12 wk
Anemia (transfusion-independent)	Grade ≥ 2 anemia (Hb < 10 g/dL)	An increase in Hb level of at least 2 g/dL that is maintained for ≥ 12 wk
Anemia (transfusion-dependent)	Transfusion of a minimum of 6 units of PRBC in the 12 wk before the start of treatment with the most recent transfusion occurring in the previous 4 wk. RBC transfusions are only considered as part of the baseline criteria if they are administered for an Hb level ≤ 8.5 g/dL and not associated with bleeding, hemolysis, or therapy	Transfusion independence for ≥ 12 wk and maintenance of a minimal Hb level of 8.5 g/dL at the end of the 12 wk period of response duration
Thrombocytopenia (transfusion-independent)	Grade ≥ 2 thrombocytopenia ($< 75 \times 10^9/L$)	A minimum 100% increase in the platelet count and an absolute platelet count increase of at least $50 \times 10^9/L$ and no need for platelet transfusions for ≥ 12 wk

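### For a fall from baseline Grade 2 to Grade 3 neutropenia, the hold rule and the baseline-cytopenia sentence of Table 1 give different answers

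*Combined protocol and SAP*

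**What the plan says.** The neutropenia paragraph of Section 4.2.5 and the first sentence of the hematologic Grade 3-4 cell of Table 1 carry the same instruction: "The dose of SGN-35 should be held for Grade 3 or 4 neutropenia until resolution to baseline or Grade 2 or lower". Neither makes an exception for a patient who was already neutropenic at entry, beyond allowing recovery to baseline as an end to the hold.

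Further down the same cell, after the sentence on anemia ("Dose interruption for anemia will not be undertaken"), Table 1 adds a sentence that opens with a baseline condition, "If patients have Grade 2 to 3 of these events at baseline only Grade 4 cytopenias suspected to be related to study drug"; its consequence in full is "only Grade 4 cytopenias suspected to be related to study drug will be considered as hematologic toxicity". The Section 4.2.5 text has no counterpart to this sentence.

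The scope of the table is set in Section 4.2.5, which says that Table 1 "describes the recommended dose modifications for study treatment-associated toxicity (toxicity with suspected relationship to SGN-35". A footnote deals with one further cytopenia: "Patients who develop Grade 3 or 4 lymphopenia may continue study treatment without interruption".

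The laboratory inclusion criteria in Section 3.3.2 cover transaminases, direct bilirubin, creatinine and creatinine clearance. They set no minimum neutrophil count.

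**The concern.** Table 1 governs toxicity. If an event is declared not to be a hematologic toxicity, a site can reasonably conclude that nothing in the table applies to it. For a patient with Grade 2 neutropenia at baseline, the later sentence does this for a fall to Grade 3. The hold sentence, higher in the same cell and repeated in the text, names Grade 3 neutropenia as a reason to hold.

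Two sites reading the same cell could therefore treat the same blood count differently, one holding the infusion and the other giving it. More than one center takes part (Sections 8.1.1 and 8.2.2), so this is a practical risk. It bears on patient safety and on dose received. It also bears on the summaries of exposure, dose reduction and reasons for dose change planned in Section 7.3, where a difference between sites could reflect how the table was read and not what the drug did.

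**Working it through.** No sample size, power or error rate is involved, and the plan gives no figure to reproduce. The check applies each sentence to each combination of baseline grade and on-treatment grade of neutropenia, taking the event as suspected to be drug-related.

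**Rule A** (Section 4.2.5 text and first sentence of the Table 1 cell): hold at Grade 3 or 4; the hold ends at baseline or at Grade 2 or better.

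**Rule B** (later sentence of the same cell): with Grade 2 or 3 at baseline, only a drug-related Grade 4 event is a hematologic toxicity.

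| Baseline | On treatment | Rule A | Rule B | Conflict? |
|---|---|---|---|---|
| Grade 0-1 | Grade 3 or 4 | Hold | Does not apply | No |
| Grade 2 | Grade 3 | Hold until Grade 2 | Not a toxicity, so outside Table 1 | **Yes** |
| Grade 3 | Grade 3 | Already at baseline, so the hold ends at once | Not a toxicity | No, in practice |
| Grade 2 or 3 | Grade 4 | Hold | Counts as toxicity | No |

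One row gives two answers.

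Three features of the text keep that row from resolving itself:

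1. Nothing states that Rule B overrides Rule A, and Rule A already has a baseline provision of its own (recovery to baseline). How the two provisions combine is not explained.
2. The Section 4.2.5 text gives Rule A alone. A site working from the text would not meet Rule B.
3. The events in Rule B are not named. The sentences before it in the cell concern neutropenia and anemia, while its consequence speaks of cytopenias in general.

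**How many patients.** This would need the share of patients with Grade 2 neutropenia at baseline and, among them, the proportion who fall to Grade 3. The documents give neither. What can be said is that the entry criteria do not keep such patients out.

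**The case against.** The strongest reply is that the cell states a general rule followed by an exception. Table 1 is limited to drug-related toxicity, and Rule B narrows what counts as toxicity for patients who arrive cytopenic. Anemia never interrupts dosing, so an exception confined to anemia would change no dosing decision; its only evident dosing effect is on the neutropenia hold. The wording is also soft: the hold is phrased as something that should be done, and the table is described as recommended. This reading is plausible and may be what was intended. However, it has to be inferred, and the Section 4.2.5 text contradicts it by omission. The point therefore stands as a need to reconcile, not as proof that either rule is a mistake.

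Three stronger readings are tempting, and the documents do not support them.

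- A reader might infer that Grade 4 thrombocytopenia is classed as a toxicity yet left with no dosing action. The word does not occur in Section 4.2.5 or Table 1. The sentence on cytopenias is conditional on baseline grade, and its reach to platelets is unclear. Section 4.2.5 also allows dose reduction according to type and severity of toxicity, and a delay of up to 30 days for recovery; neither is limited to neutropenia. What is missing is a platelet-specific instruction, which is an omission and not a contradiction.
- A reader might take the lymphoma rates in Section 1.2 (Grade 3 neutropenia 13%, Grade 4 7%), add them to 20%, and expect 0.20 × 11 = 2.2, or about 2 of 11 patients, and 0.20 × 26 = 5.2, or about 5 of 26. Those would be all Grade 3-4 neutropenia. The Grade 4 part raises no conflict, and the Grade 3 part counts only if baseline was Grade 2, a share not given for either population. The 26 also depends on a later amendment (Section 7.8).
- A reader might cite the Appendix G organ-damage entry "Baseline grade ≥ 3 ANC" as showing that affected patients are common. It describes baseline Grade 3 or worse, and the conflict needs baseline Grade 2.

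**Conclusion.** The concern holds for one transition: neutropenia going from Grade 2 at baseline to Grade 3 on treatment. There the plan both holds SGN-35 and treats the event as outside the table that governs holds. It rests on two assumptions: that the unnamed events include neutropenia, and that an event declared not to be a toxicity falls outside Table 1, as the table's stated scope implies. If the first fails, the baseline sentence has little evident purpose for dosing and still needs clarifying.

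The size in patients cannot be estimated from the documents. The primary response endpoint and the two-stage decision rule are not affected. Nor is the safety hold triggered by 4 of 11 patients, which counts non-hematologic toxicity only. The point should be settled because it bears on patient safety and on consistent dosing across sites. No view is taken on which rule is clinically right.

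**What to change.** Reconcile the neutropenia paragraph of Section 4.2.5 with the hematologic Grade 3-4 cell of Table 1:

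- State one neutropenia rule by baseline grade, in the same words in both places, so that a fall from baseline Grade 2 to Grade 3 has a single answer. The sponsor chooses that answer.
- Replace the undefined reference to events with the names of the cytopenias that the baseline sentence covers. If it is an exception to the hold, say so.

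As a side note only, the Grade 3-4 cell has no platelet-specific instruction. While the cell is being edited, the sponsor may wish to say whether the general term for cytopenias includes thrombocytopenia.

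The cost is a few sentences in Section 4.2.5 and one table cell. No new data are needed: hematology is already drawn at screening and in every cycle (Section 4.8.1).

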4.3 Treatment Discontinuation

Any patient discontinuing study medication prematurely must have the reason categorized on the CRF as one of the following:

1. adverse event(s)
2. abnormal laboratory value(s)
3. abnormal test procedure result(s)
4. unsatisfactory therapeutic effect
5. subject's condition no longer requires study treatment
6. protocol violation
7. subject withdrew consent
8. lost to follow-up
9. administrative problems
10. death

Patients who discontinue the study due to a study drug-related adverse event must be followed weekly for four weeks, or until resolution or stabilization of the event, whichever occurs first.

Patients discontinuing prematurely are to be followed every 6 months for survival until study closure or death of the patient.

4.4 Concomitant therapy

In general, the use of any concomitant medication/therapies deemed necessary for patient supportive care and safety are permitted provided they are documented in the patient records. A list of medications which may be used to treat mediator-related symptoms are listed in **Appendix D**. All medications taken within 30 days of the first dose of study drug and all concomitant medications/therapies must be recorded on the Concomitant/Non-Drug Therapy CRF.

Women will avoid breast-feeding, and all women of childbearing potential will be required to use barrier contraception for the duration of the study and for 3 months post study.

Other anti-cancer agents including chemotherapy, radiation therapy, or biologic response modifiers are not permitted during the study. No other investigational drug is allowed during the study. Hematopoietic growth factors are not permitted during study (except G-CSF for neutropenic fever). Prophylaxis may be used for the prevention of nausea and vomiting and is at the discretion of the investigator.

Other anti-cancer agents including chemotherapy, radiation therapy, or biologic response modifiers are not permitted during the study. The exception is the use of hydroxyurea to control a proliferative leukocyte count related to a concurrent myeloid neoplasm (eg, CMML, or other MDS/MPN, or MPN associated with advanced SM). No other investigational drug is allowed during the study. Hematopoietic growth factors are not permitted during the study.

(except G-CSF for neutropenic fever). The exception is the use of erythropoiesis stimulating agents (with or without IV iron) in patients who are Jehovah's witnesses and for religious reasons are not permitted to undergo treatment with blood products. Prophylaxis may be used for the prevention of nausea and vomiting and is at the discretion of the investigator.

During treatment with SGN-35, glucocorticoids can be used in the event of appropriate need, as outlined in **Appendix D**, "Mediator Drugs to Ameliorate Symptoms Related to Systemic Mastocytosis."

4.4.1 Cytochrome P450 Metabolism and Drug- Interactions

Because SGN-35 is primarily metabolized by CYP3A enzymes, any drug known to inhibit or induce CYP3A4 will likely interact with SGN-35. The extent is normally more profound with CYP3A4 inhibitors than with inducers. Where possible, investigators should refrain from choosing to administer CYP3A4/5 inducers to patients on study prior to initiation, and during treatment with SGN-35. In particular, investigators should NOT give the combination of two such agents in patients receiving SGN-35, such as antifungal azoles plus erythromycin or azithromycin. In addition, prior to initiation of SGN-35, and during treatment, concomitant use of the following CYP3A4 *substrates* is discouraged: alprazolam, astemizole, atorvastatin, cervistatin, chlorpheniramine, diazepam, indinavir, lovastatin, midazolam, nelfinavir, progesterone, ritonavir, saquinavir, tacrolimus, terfenadine, triazolam, and the CYP3A4 inducers modafinil, rifabutin, and rifampin. A list of inhibitors and inducers is provided in **Appendix E**.

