APPENDIX E

List of CYP3A Inhibitors and Inducers

CYP3A4/5 Inhibitors

Amiodarone	Diethyldithiocarbamate	Grapefruit juice	Norfloxacin	Sertindole
Anastrozole	Diltiazem	Indinavir	Omeprazole	Sertraline
Azithromycin	Dirithromycin	Isoniazid	Oxiconazole	Troglitazone
Cannabinoids	Disulfiram	Itraconazole	Paroxetine	Troleandomycin
Cimetidine	Entacapone	Ketoconazole	Propoxyphene	Valproic Acid
Clarithromycin	Erythromycin	Metronidazole	Quinidine	Verapamil
Clotrimazole	Ethinyl estradiol	Miconazole	Quinine	Zafirlukast
Cyclosporine	Fluconazole	Nefazodone	Quinupristin	Zileuton
Danazol	Fluoxetine	Nelfinavir	Ranitidine	
Delavirdine	Fluvoxamine	Nevirapine	Ritonavir	
Dexamethasone	Gestodene	Norfluoxetine	Saquinavir	

CYP3A4/5 Inducers

Carbamazepine	Nafcillin	Phenylbutazone	Rifampin	Troglitazone
Dexamethasone	Nelfinavir	Phenytoin	Rofecoxib (mild)	
Ethosuximide	Nevirapine	Primidone	St. John's wort	
Glucocorticoids	Oxcarbazepine	Progesterone	Sulfadimidine	
Griseofulvin	Phenobarbital	Rifabutin	Sulfinpyrazone	

A study of brentuximab vedotin (SGN-35) in CD30-positive systemic mastocytosis with or without an associated hematological clonal non-mast cell lineage disease (AHNMD)

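### Section 4.4.1 ranks CYP3A4 inhibitors as the larger interaction, yet its general avoidance advice names only inducers and its combination rule is illustrated with inhibitors

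*Combined protocol and SAP*

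**What the plan says.** Section 4.4.1 makes its case in consecutive sentences.

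- Scope: "any drug known to inhibit or induce CYP3A4 will likely interact with SGN-35".
- Relative size: "The extent is normally more profound with CYP3A4 inhibitors than with inducers".
- General advice, qualified as applying where possible: "investigators should refrain from choosing to administer CYP3A4/5 inducers to patients on study prior to initiation, and during treatment with SGN-35".
- Combination rule, introduced as a particular case of that advice: investigators "should NOT give the combination of two such agents in patients receiving SGN-35, such as antifungal azoles plus erythromycin or azithromycin".
- Drugs discouraged by name: a list labelled as CYP3A4 substrates, "and the CYP3A4 inducers modafinil, rifabutin, and rifampin".
- Reference: "A list of inhibitors and inducers is provided in" Appendix E, with no instruction attached.

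Appendix E is two lists of drugs, one headed "CYP3A4/5 Inhibitors" and one for inducers, and contains no rule of its own. Section 4.4 is permissive in general: supportive medication judged necessary may be given if it is documented.

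**The concern.** The avoidance sentence fits neither the sentence before it nor the sentence after it. The sentence before names inhibitors as the stronger interaction. The sentence after gives examples that are all inhibitors. The class named in between is inducers.

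An investigator deciding on a concomitant drug would act on this sentence. Read literally, it gives no general caution about a single drug from the class that the protocol itself calls the larger concern. Such drugs are likely to come up in this trial. Appendix D puts H2 antagonists at step 1 for several symptoms and also lists proton-pump inhibitors. Appendix E classes cimetidine, ranitidine and omeprazole as inhibitors (I take the first two to be H2 antagonists and the third a proton-pump inhibitor; the documents do not say so). What is at stake is whether sites handle these drugs alike and as the sponsor intended.

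**Working it through.** The plan gives no figure on this point, so there is none to reproduce. The check compares the sentences of Section 4.4.1 with the lists in Appendix E.

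**Step 1: class of each example in the combination rule**

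| Example | Inhibitor list | Inducer list |
|---|---|---|
| Erythromycin | yes | no |
| Azithromycin | yes | no |
| Azoles (clotrimazole, fluconazole, itraconazole, ketoconazole, miconazole, oxiconazole) | yes, all six | none |

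No example belongs to the class named in the sentence that the rule is meant to particularise.

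**Step 2: what 'such agents' can refer to**

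- *Inducers, the nearest antecedent.* The examples then fall outside the rule's own class.
- *Any inhibitor or inducer, from the scope sentence.* The examples then fit. The rule is, however, wider than the advice it is said to be a case of, and that advice still does not mention a single inhibitor.

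Under both readings, single inhibitors as a class have no general instruction.

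**Step 3: how many listed drugs the avoidance sentence reaches**

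Counts of entries as printed in Appendix E:

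- Inhibitors: 52
- Inducers: 21
- In both lists: 4 (dexamethasone, nelfinavir, nevirapine, troglitazone)
- Distinct entries: 52 + 21 − 4 = 69

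The sentence names inducers, so it reaches 21 entries, including the 4 in both lists. It does not reach 69 − 21 = 48, which agrees with 52 − 4 = 48 inhibitor-only entries.

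**Step 4: allow for drugs discouraged by name**

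Four drugs in the substrate list of Section 4.4.1 are inhibitors in Appendix E: indinavir, nelfinavir, ritonavir and saquinavir. Nelfinavir is already among the 4 in both lists, so three more come off: 48 − 3 = 45. These 45 have no single-agent wording, general or by name.

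**Step 5: look for a passage that resolves it**

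Section 4.4 gives no general rule on inhibitors. The closing sentence of Section 4.4.1 refers to both lists without saying what to do with either. There are also two small mismatches between text and appendix: modafinil is called an inducer in Section 4.4.1 but is not in Appendix E's inducer list, and progesterone is labelled a substrate in one place and an inducer in the other.

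**The case against.** The strongest reply is that nothing here is a strict contradiction. Saying that inhibitors usually have the larger effect is compatible with advising against inducers, since both are said to interact. The phrase 'such agents' can be traced back to the scope sentence. The advice is soft and sits within a permissive section that requires all concomitant medication to be recorded. Much of this stands: the rationale and the advice can both be true, and the advice is not a prohibition. The reply does not explain why the advice omits the class ranked as more important, and the alternative antecedent leaves that omission in place.

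A reader might infer more than the documents support, in four ways.

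- *That a single inhibitor carries no restriction at all.* Four inhibitors are discouraged by name. The accurate statement concerns the class.
- *That sites cannot tell which class any of the advice covers.* The avoidance sentence plainly says inducers, and Appendix E labels both classes. What is unclear is the scope of the combination rule and whether the silence on single inhibitors is deliberate.
- *That the word for inducers is simply a slip.* This is possible, but the section also discourages three inducers by name, and nothing in the documents settles what was meant.
- *That the wording distorts exposure or the toxicity hold in the first 11 patients (Section 4.2.5).* The documents give no size for any CYP3A4 interaction and no expected use of inhibitors, so this has no support.

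**Conclusion.** The inconsistency is real, and no other section resolves it. The rationale ranks inhibitors first, the general advice names only inducers, and the combination rule is illustrated wholly with inhibitors. As worded, 48 of the 52 inhibitor entries lie outside the general advice, and 45 of them are not discouraged by name either.

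The counts assume that Appendix E is complete as printed and take each entry as one item, although a few entries, such as cannabinoids and glucocorticoids, are groups. The defect itself does not depend on the exact count.

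The point is minor statistically. The two-stage design in Section 7.8, its error rates, the populations in Section 7.1 and the primary analysis in Section 7.5 are unaffected. It still merits correction because the sentence is an instruction on patient care rather than background.

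**What to change.** Reconcile four elements: the statement of relative effect, the avoidance sentence, the combination rule with its examples, and Appendix E. Name the class or classes covered explicitly, replace 'such agents' with the class meant, and make the examples members of that class. If the silence on single inhibitors is intended, say so. Align the classification of modafinil and progesterone in the same pass. Which class to restrict, and how firmly, is the sponsor's clinical decision; no rule is proposed here.

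The drafting cost is a few sentences. Section 8.3.1 requires ethics committee approval for any amendment that is not administrative, so the change is best included in the next amendment, for example the one that Section 7.8 foresees if the second stage opens, unless the sponsor judges that sites need clarification sooner.
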